8.5. Pharmacokinetics

Serum samples will be used to evaluate the PK of JNJ-64565111. Serum collected for PK may additionally be used to evaluate safety or efficacy aspects that address concerns arising during or after the study period. Genetic analyses will not be performed on these serum samples. Subject confidentiality will be maintained.

Evaluations

Refer to the Schedule of Activities for the timing and frequency of all sample collections.

Blood collections for PK assessments should be kept as close to the specified time as possible.

Venous blood samples will be collected from all subjects according to the Schedule of Activities for determination of serum trough concentrations of JNJ-64565111 to assess attainment of steady-state concentrations. In addition, a non-trough (peak) sample on Day 4 will be collected from all subjects, as well as a post-treatment sample at 16 weeks from all subjects. On the days of the trough clinic visits at which PK samples are to be obtained, subjects are not to inject the study drug before arriving at the clinic.

The non-trough PK sampling time point was prospectively optimized for population-based PK analyses. In addition to the trough samples and a post-treatment sample in all subjects, all subjects will have 1 additional visit (Day 4±1-day sampling window) to collect a non-trough PK sample.

The exact dates and times of previous study drug injection and blood sampling for PK must be recorded in the eCRF or laboratory requisition form for all PK samples.

See the laboratory manual for information regarding handling of biologic samples.

Pharmacokinetic Analytical Procedures

Serum samples will be analyzed to determine concentrations of JNJ-64565111 using a validated, specific, and sensitive immunoassay method by or under the supervision of the sponsor.

Parameters

Serum concentrations at each time point of measurement will be evaluated by descriptive statistics, including arithmetic mean, geometric mean, standard deviation, coefficient of variation, geometric coefficient of variation, minimum, maximum, and median.

8.6. Pharmacodynamics

Pharmacodynamics are part of efficacy, see Section 8.1, Efficacy Assessments.

8.7. Genetics

Pharmacogenomics/Genetics are not evaluated in this study.

8.8. Archive Samples for Exploratory Biomarker Research

Archived samples may be used for future analysis of biomarkers related to the safety and/or efficacy of JNJ-64565111, and/or the study of T2DM, obesity, and its complications.

8.9. Health Economics/Medical Resource Utilization and Health Economics

Health Economics/Medical Resource Utilization and Health Economics parameters are not evaluated in this study.

8.10. Further Assessments

8.10.1. Immunogenicity Assessments

The detection and characterization of anti-JNJ-64565111 antibodies will be performed using a validated assay method by or under the supervision of the sponsor. All samples collected for detection of anti-JNJ-64565111 antibodies will also be evaluated for JNJ-64565111 serum concentration to enable interpretation of the antibody data.

Anti-JNJ-64565111 antibodies will be evaluated in serum samples collected from all subjects according to the Schedule of Activities. Additionally, serum samples should also be collected at the final visit from subjects who are discontinued from treatment.

Serum samples will be screened for antibodies binding to JNJ-64565111 and the titer of confirmed positive samples will be reported. Other analyses may be performed to verify the stability of antibodies to JNJ-64565111 and/or further characterize the immunogenicity of JNJ-64565111.

8.10.2. Survey on Experience with Self-injection of Study Drug

A survey designed to assess subject satisfaction with the experience of self-administering study drug will be given to English-speaking subjects at Week 6.

9. STATISTICAL CONSIDERATIONS

Statistical analysis will be done by the sponsor or under the authority of the sponsor. A general description of the statistical methods to be used to analyze the efficacy and safety data is outlined below. Specific details will be provided in the Statistical Analysis Plan.

9.1. Statistical Hypotheses

The goal of the primary efficacy analysis is to determine if there is treatment difference in the percentage reduction in body weight from baseline between JNJ-64565111 treatment groups and the placebo group at Week 12. The null hypothesis is that there is no difference between the treatment groups in the percentage reduction in body weight. The alternative hypothesis is that there is a greater percentage reduction in body weight in the JNJ-64565111 treatment groups compared with placebo group.

9.2. Sample Size Determination

A total of 188 subjects will be randomly assigned in this study with 47 subjects per group allocated to each of the 4 treatment groups. Sample size was determined based on assessing the primary hypothesis that treatment with JNJ-64565111 at 1 or more dose levels for 12 weeks leads to greater percentage reduction in body weight compared with placebo.

Assuming a common SD of 4% with respect to percent change in body weight at Week 12 and a 2-sided type I error rate of 0.05, it is estimated that a sample size of 47 randomly assigned subjects per group will have approximately 90% power to detect a treatment difference of 2.7%.

9.3. Populations for Analyses

For purposes of analysis, the following populations are defined:

Table 5: Subject Population Definitions

Population	Description
Enrolled	All subjects who sign the ICF
ITT analysis set	all subjects who are randomly assigned to a treatment group and have a baseline measurement of body weight
mITT analysis set	all ITT subjects who have at least 1 post-baseline measurement of body weight within 7 days following a dose of study drug and before initiation of any rescue therapy
Completers' analysis set	of all mITT subjects who have completed 12 weeks of double-blind treatment (ie, documented in the eCRF by the investigators that the subject has completed participation in the study through the Week 12 visit) and without initiation of glycemic rescue therapy
Safety analysis set	all randomized subjects who have received at least one dose of study drug

Key: eCRF=electronic case report form; ICF=informed consent form; ITT=intent-to-treat; mITT=modified intent-to-treat.

The primary efficacy analysis, to demonstrate the superiority of JNJ-64565111 compared with placebo on percentage reduction in body weight from baseline to Week 12, as well as all secondary efficacy analyses, will be based on the modified intent-to-treat (mITT) analysis set and will include only those measurements taken up to and including the last dose of study drug plus 7 days and prior to initiation of any glycemic rescue therapy. A secondary analysis of the primary and secondary efficacy endpoints will be based on the intent-to-treat (ITT) analysis set. This analysis will include all measurements. Sensitivity analyses based on the completers' analysis set will also be performed for the primary endpoint.

Efficacy data will be analyzed according to the initial randomization assignment, regardless of the actual treatment received. Safety data will be analyzed according to the predominant treatment received, in the event that a subject receives a treatment other than that to which he/she is randomly assigned.

9.4. Statistical Analyses

9.4.1. Efficacy Analyses

All hypotheses will be tested 2-sided at a 5% significance level unless otherwise notes.

Primary Efficacy Endpoint

The primary efficacy endpoint will be the percentage change in body weight between JNJ-64565111 and placebo from baseline to Week 12.

The primary efficacy endpoint will be analyzed based on the mITT analysis set using a mixed model for repeated measures (MMRM). The analysis will use the observed data through Week 12 while on treatment (up to the last dose of study drug plus 7 days) and prior to rescue medication. The analysis model will include the fixed, categorical effects of treatment, visit, and treatment-by-visit interaction, as well as the continuous covariates of baseline body weight and baseline-by-visit interaction. An unstructured covariance will be used to model the within-patient errors. The treatment comparisons will be made between each of the JNJ-64565111 treatment groups and placebo at Week 12 based on this model.

A secondary analysis of the primary endpoint will be based on the ITT analysis set and will employ pattern mixture models using multiple imputation methods. This analysis will use all observed data, including the measurements off treatment. Responses for subjects who discontinued from the study earlier than Week 12 will be imputed based on subjects who discontinued treatment prematurely but subsequently provided off-treatment measurements. The imputation will be done within randomized treatment groups. Data will be analyzed using the same model as in the primary analysis. The treatment comparisons between each of the JNJ-64565111 treatment groups and placebo will be made at Week 12. Details of this approach will be provided in the statistical analysis plan (SAP).

Finally, the primary efficacy endpoint will be analyzed based on the completers analysis set. Additional analysis using a Multiple Comparison Procedure – Modeling approach ([Bornkamp 2009](#); [Pinheiro 2014](#)) will be performed to explore the dose-response relationship.

Secondary Efficacy Endpoints

Secondary efficacy analyses at Week 12 will include the absolute change in body weight from baseline and the proportion of subjects with $\geq 5\%$ weight loss.

The absolute change in body weight from baseline at Week 12 will be analyzed with an MMRM model similar to the primary efficacy endpoint based on the mITT analysis set.

The proportion of subjects with $\geq 5\%$ weight loss will be analyzed longitudinally using a generalized linear mixed model based on the mITT analysis set. The analysis will use the observed data through Week 12 while on treatment (up to the last dose of study drug plus 7 days) and prior to rescue medication. The model will include the fixed, categorical effects of treatment, visit, and treatment-by-visit interaction, as well as the continuous covariates of baseline weight, and baseline-by-visit interactions. An unstructured covariance will be used to model the within-patient errors. The odds ratio and associated p-value for the treatment comparison between each of the JNJ-64565111 treatment groups versus placebo at Week 12 based on this model will be provided.

A secondary analysis of the secondary endpoints will be based on the ITT analysis set and will employ pattern mixture models using multiple imputation methods based on information from retrieved dropouts as described above. For the proportion of subjects with $\geq 5\%$ weight loss, response status will be determined from the imputed continuous response based on subjects who discontinued treatment prematurely but subsequently provided off-treatment measurements.

Multiplicity Adjustment

The type I error will be strongly controlled at $\alpha=5\%$ for each of the primary endpoint and secondary endpoints. The Hochberg approach will be used to adjust the multiplicity of the comparisons of each of the JNJ-64565111 doses versus placebo for each endpoint.

Exploratory Endpoints

The continuous exploratory efficacy endpoints will be analyzed using a MMRM model similar to the model used to analyze the primary efficacy endpoint based on the mITT analysis set. The categorical exploratory efficacy endpoints will be analyzed using a generalized linear mixed model similar to the model used to analyze the proportion of subjects with $\geq 5\%$ weight loss.

9.4.2. Safety Analyses

The evaluation of safety will be based on the incidence of adverse events and hypoglycemia episodes, and changes in clinical laboratory test results and vital sign results (blood pressure, pulse rate). The safety analyses will be based on the safety analysis set including all data, regardless of the initiation of glycemic rescue therapy (ie, including data after initiation of rescue therapy). Additional analysis of hypoglycemia will be performed based on the data prior the initiation of glycemic rescue therapy only. Summaries of adverse events, clinical laboratory test results, and vital sign results will be provided by treatment group. There will be no imputation of missing values for clinical safety laboratory test results, and vital sign measurements.

Adverse Events

The verbatim terms used in the eCRF by investigators to identify adverse events will be coded using the Medical Dictionary for Regulatory Activities (MedDRA). Treatment-emergent adverse events are adverse events with onset during the treatment phase or that are a consequence of a pre-existing condition that has worsened since baseline. All reported adverse events will be included in the analysis. For each adverse event, the percentage of subjects who experience at least 1 occurrence of the given event will be summarized by treatment group. In addition, comparisons between treatment groups will be provided if appropriate.

Summaries, listings, datasets, or subject narratives may be provided, as appropriate, for those subjects who die, who discontinue study drug due to an adverse event, or who experience a severe or a serious adverse event.

For each adverse event, the percentage of subjects who experience at least 1 occurrence of the given event will be summarized by treatment group. The percentage of subjects with specific treatment-emergent adverse events (TEAEs) will be summarized by severity and relationship to study drug, as classified by the investigator, by treatment group. The dose-response relationship of dose levels on TEAE will be assessed, assuming that the incidence rates of TEAE will be monotonic with respect to dose levels. A listing for non-TEAEs will be provided.

Hypoglycemic events will be classified as severe, documented symptomatic, probable symptomatic and asymptomatic. The primary hypoglycemic analysis of interest will be all documented hypoglycemic events regardless of the presence of symptoms (ie, documented symptomatic and asymptomatic hypoglycemia) plus all severe hypoglycemic events. For each type of hypoglycemia, the percentage of subjects with at least one event will be summarized by treatment group. The differences in percentage (JNJ-64565111 versus placebo) and their 2-sided 95% confidence intervals will be estimated.

Hypoglycemic events are collected on a separate eCRF and also collected on the Adverse Event eCRF (for all such events considered as adverse events by the investigator). The primary analysis of hypoglycemia will be based upon data from the hypoglycemia eCRF (and not from the adverse event database). No reconciliation of hypoglycemia data from the Adverse Event eCRF and the hypoglycemic eCRF will be performed (except to assure that all adverse events of hypoglycemia are also recorded on the hypoglycemia eCRF).

Further analyses, to be described in the SAP for this study which will be finalized before the subject is randomized, will be conducted on the prespecified adverse events for which additional information is collected from the investigators (refer to Section 8.2, Safety Assessments), and on other adverse events.

Clinical Laboratory Tests

Laboratory data will be summarized by type of laboratory test. Normal reference ranges will be provided. Criteria for markedly abnormal laboratory values will be prespecified in the SAP. The percentage of subjects with markedly abnormal results will be summarized for each laboratory

analyte. Descriptive statistics will be reported for each laboratory analyte at baseline and at each scheduled time point and for change from baseline.

Resting Vital Signs (Pulse, Blood Pressure)

Descriptive statistics of pulse rate and sitting blood pressure (systolic and diastolic) values and changes from baseline will be summarized at each scheduled time point. The percentage of subjects with values beyond clinically important limits will be summarized.

Physical Examination

Physical examination findings will not be summarized except when reported as an adverse event.

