### **Exploratory Analyses**

Additional analysis using a MCP-Mod (Multiple Comparison Procedure – Modelling) approach will be performed to explore the dose response relationship.

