## **6. SAFETY**

All safety analyses and summaries will be based on the safety analysis set (Section 2.2.3). Safety data will be analyzed according to the predominant treatment received, in the event that a subject received a treatment other than that to which they were randomly assigned to receive. The predominant treatment is defined as the treatment to which the subject was exposed for the greatest duration during the double-blind treatment phase.

The evaluation of safety will be based on the incidence of adverse events, hypoglycemia episodes, and changes in clinical laboratory test results and vital sign results (blood pressure and pulse rate). The safety analyses will be based on the safety analysis set including all data, regardless of the initiation of glycemic rescue therapy (ie, including data after initiation of rescue therapy). Additional analysis of hypoglycemia will be performed based on the data prior the initiation of glycemic rescue therapy only. There will be no imputation of missing values for clinical laboratory test results and vital sign measurements in the safety analyses and there will be no hypothesis testing for results from safety analyses. Summaries of AEs, clinical laboratory test results, and vital sign results will be provided by treatment group and for the combined JNJ-64565111 treatment group.

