### **6.1. Adverse Events**

The verbatim terms used in the CRF by investigators to identify adverse events will be coded using the Medical Dictionary for Regulatory Activities (MedDRA). A treatment-emergent AE (TEAE) is defined as an adverse event with an onset after the initiation study medication and before the last study medication date of the double-blind (12-week) treatment phase plus 35 days. AEs with a start date prior to initiation of double-blind study medication which are subsequently reported to have either an increase in intensity or change in attribution in relationship to study medication (i.e., no attribution to possible, probably, very likely) after the initiation of double-blind study medication will also be considered as TEAEs.

If the event occurs on the day of the initial administration of study agent, and either event time or time of administration are missing, then the event will be assumed to be treatment emergent. If the event date is recorded as partial or completely missing, then the event will be considered to be treatment emergent unless it is known to be prior to the first administration of study agent based on partial onset date or resolution date. All reported treatment-emergent adverse events will be included in the analysis. For each adverse event, the number and percentage of subjects who experience at least 1 occurrence of the given event will be provided by preferred term, grouped by system organ class (SOC), and presented by treatment group. In addition, comparisons between treatment groups may be provided as needed.

Summary tables will be provided for:

- AEs
- AEs leading to discontinuation
- Drug-related AEs
- Drug-related AEs leading to discontinuation
- Serious AEs (SAEs)
- Serious AEs leading to discontinuation
- Serious drug-related AEs leading to discontinuation and deaths
- AEs by system organ class
- AEs by severity
- AEs by relationship to study agent: related (which includes possibly related, probably related and very likely related, as reported by the investigator) and not related (which includes not related and doubtfully related, as reported by the investigator)
- AEs by the action taken regarding the study medication
- AEs by outcome

In addition to the summary tables, listings will be provided for subjects who had:

- SAEs
- AEs leading to discontinuation

Incidence of other treatment-emergent adverse events of special interest will be summarized.

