Deaths will be displayed by actual treatment received. Frequencies for the following parameters will be included in the summary table:

- Number of subjects who died
- Cause of death
- Relationship to study agent (yes/no)

A listing of subjects who died will be provided.

As a screening tool, the 95% CIs for percentage difference between JNJ-64565111 and placebo will be provided for the AEs which are reported in at least four or more subjects in any treatment group during the treatment phase. Four (rule-of-4) is chosen based on the recommendation from the Safety, Planning, Evaluation, and Report (SPERT). No multiplicity adjustment will be applied. The exclusion of “0” in the 95% CI around the difference in incidence (JNJ-64565111 compared to placebo) for a particular AE does not necessarily imply that the higher incidence is related to drug. The intent of providing the 95% CIs is as a filter to identify AEs that require additional assessment.

Adverse events that are identified by the above screening procedure will be subject to further evaluation. The additional assessment may include some or all of the following, comparing JNJ-64565111 and placebo:

1. Investigator assessed relationship of AE to study drug, investigator assessed intensity of AE
2. Time to AE relative to start of double-blind study medication, duration of AE, action taken on study drug/occurrence of AEs leading to discontinuation
3. Other relevant safety information such as observations in other trials.

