## 7. PHARMACOKINETICS/IMMUNOGENICITY/PHARMACODYNAMICS

### 7.1. Pharmacokinetics

Pharmacokinetics (PK) samples for measuring serum JNJ-64565111 concentrations will be collected from all subjects at the specified visits as shown in the schedule of events of the protocol. In all subjects randomly assigned to JNJ-64565111 or matching placebo, venous blood samples will be collected according to the Time and Events Schedule for determination of serum trough concentrations of JNJ-64565111 to assess attainment of steady state concentrations. In addition, a sample at the 4-week safety follow-up visit will also be collected in all subjects. On the days of the trough clinic visits at which PK samples are to be obtained, subjects are not to inject the study drug before arriving at the clinic. In addition to the trough samples and a post-treatment sample in all subjects, all subjects will have 1 additional visit (Day 4 ± 1 day sampling window) to collect a non-trough PK sample. All PK evaluations will be based on the PK analysis set. No imputation for missing concentration data will be performed.

The data analysis of trough and non-trough serum JNJ-64565111 concentrations includes the following:

- Tabular summary of serum JNJ-64565111 concentrations at each PK visit by treatment group.

- Tabular summary of serum JNJ-64565111 concentrations at each visit by treatment group and body weight tertiles at baseline.
- Proportion of subjects without detectable serum JNJ-64565111 concentration at each visit by treatment group.
- Median trough, non-trough, and week 16 temporal serum JNJ-64565111 concentrations plotted over time by treatment group.
- Median trough serum JNJ-64565111 concentrations plotted over time by treatment group to assess attainment of steady-state.

In addition, the relationship between serum JNJ-64565111 concentrations, and antibody to JNJ-64565111 status, safety and efficacy may be explored using graphical displays.  $\geq 5\%$  and  $\geq 10\%$  weight loss response rates and % weight loss at Week 12 will be presented in a bar graph by the corresponding serum JNJ-64565111 concentration quartiles at Week 12 for subjects treated with JNJ-64565111.

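### The protocol commits to a dose-response assessment of treatment-emergent adverse events, but the SAP does not carry it forward, so tolerability has no prespecified dose-response estimate

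*Protocol*

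**What the plan says.** Protocol 9.4.2 (Adverse Events) states: "The dose-response relationship of dose levels on TEAE will be assessed, assuming that the incidence rates of TEAE will be monotonic" with respect to dose. The same subsection separately allows comparisons between treatment groups where appropriate, so the protocol treats the two as different analyses. Protocol section 9 leaves specific methods to the SAP. The change list of Amendment 1 does not touch 9.4.2, so the commitment is current.

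SAP 6 and 6.1 provide the following for adverse events:

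- Summaries: adverse event, laboratory and vital sign "results will be provided by treatment group and for the combined" active group. The 6.1 tables cover incidence, severity, relationship, action taken, outcome and events leading to discontinuation.
- Intervals: "As a screening tool, the 95% CIs for percentage difference between JNJ-64565111 and placebo will be provided for the AEs" reported in at least four subjects in any group.
- An option: "In addition, comparisons between treatment groups may be provided as needed".
- A restriction: "there will be no hypothesis testing for results from safety analyses".

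Elsewhere, SAP 7.1 says that the relationship of serum concentration to "safety and efficacy may be explored using graphical displays". The only dose-response method in the SAP is MCP-Mod, listed under the primary efficacy endpoint in 5.2.3, which "will be performed to explore the dose response relationship".

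**The concern.** The protocol promises an analysis and gives its structural assumption, monotone incidence in dose. The SAP, where the method should appear, has nothing that matches. If the SAP is followed as written, the promised assessment need not be produced. If it is produced later, its outcomes, dose scale and model could be chosen after unblinding.

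Safety and tolerability is listed as a primary objective beside percentage weight change. Protocol 2.1 and 4.2.1 give selection of Phase 3 doses as the purpose of the trial. Protocol 4.3 reports a dose-dependent rise in gastrointestinal events, said of doses above 10 mg. Whether a similar gradient exists between 5.0 and 10 mg is a natural question for this trial, and intervals against placebo do not estimate it. Weight loss will have a modelled dose-response curve to set against dose, and tolerability will not.

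**Working it through.** **1. Comparing the documents.**

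| Element | Protocol 9.4.2 | SAP 6, 6.1, 7.1 |
|---|---|---|
| TEAE incidence by dose group | Yes | Yes, plus combined active group |
| Intervals against placebo | Not stated for adverse events generally | Yes, as a screening tool |
| Between-group comparisons | If appropriate | Optional |
| Dose-response of TEAEs, assumed monotone | Will be assessed | None specified |
| Concentration against safety | Exposure-response modelling only in 9.4.3, optional | Optional, graphical |

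The fourth row is the gap.

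**2. The plan's own figure.** The documents give no figure for TEAE dose-response. The stated power of about 90% concerns weight. It reproduces: 2.7 / (4 × √(2/47)) = 3.27, and Φ(3.27 − 1.96) = 0.905. It has no bearing on this point beyond fixing 47 subjects per arm.

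**3. What an active-dose trend could show.** All event rates below are assumptions. With doses 5, 7.4 and 10 mg, the mean is 7.467, the deviations d are −2.467, −0.067 and 2.533, and Σd² = 12.51. For a linear trend with n = 47:

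- T = n Σ d·p
- V0 = p̄(1 − p̄) n Σd²
- V1 = n Σ d²·p(1 − p)
- power ≈ Φ((T − 1.96√V0) / √V1), two-sided 5%

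| Assumed rates 5/7.4/10 mg | T | √V0 | √V1 | Power, formula | Power, simulated |
|---|---|---|---|---|---|
| 20/30/45% | 29.45 | 11.28 | 10.98 | 0.75 | 0.76 |
| 20/30/40% | 23.50 | 11.11 | 10.87 | 0.56 | 0.57 |
| 20/25/30% | 11.75 | 10.50 | 10.45 | 0.20 | 0.20 |
| 17/20/25% | 9.43 | 9.82 | 9.85 | 0.16 | 0.16 |

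By simulation, a plain 95% interval for 10 mg minus 5 mg excludes zero with probability 0.76, 0.59 and 0.21 in the first three rows. A trend has no power advantage over that comparison.

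**4. Precision of a slope.** The standard error of the logistic slope per mg is roughly 1/√V0.

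- At 20/30/40%: 1/11.11 = 0.090. Over 5 mg the half-width is 1.96 × 0.090 × 5 = 0.88, a factor of e^0.88 = 2.4. The odds ratio, 10 mg to 5 mg, is (0.40/0.60)/(0.20/0.80) = 2.67, with an interval of about 1.1 to 6.4.
- At 20/25/30%: 1/10.50 = 0.095, half-width 0.93, factor 2.5. The odds ratio is (0.30/0.70)/(0.20/0.80) = 1.71, with an interval of about 0.67 to 4.4.

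**5. What happens if placebo is included.** With doses 0, 5, 7.4 and 10 mg, d is −5.6, −0.6, 1.8 and 4.4, and Σd² = 54.32. Take 10% on placebo and a flat 30% on every active dose.

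- T = 47 × (−0.56 − 0.18 + 0.54 + 1.32) = 52.64, √V0 = 21.88, √V1 = 18.95
- Power ≈ Φ((52.64 − 42.88)/18.95) = 0.70; simulated 0.71
- The active-only trend at 30/30/30% is positive 0.05 of the time

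A four-arm trend therefore often signals a gradient when none exists among the active doses. It also adds nothing against placebo: at 10/17/20/25% it has 50% power, against 51% for the 10 mg versus placebo interval.

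**The case against.** A fair defence has five parts.

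- **Tolerability is shown across doses.** The SAP tabulates adverse events for each dose side by side, pools terms for nausea, vomiting and diarrhea (SAP 6.1, Attachment 3), and permits comparisons not limited to placebo. This stands. A reader might infer that the SAP has no analysis of tolerability across doses, or compares doses only with placebo; neither is correct. But tables contain no dose-response estimate, and an optional comparison does not discharge an analysis that the protocol lists separately as one that will be done.
- **Nothing shows a removal.** A reader might infer that the analysis was dropped without record. The amendment history records changes between SAP versions, and no previous SAP version is available, so its silence proves nothing. This stands. The supportable statement is that the SAP does not carry the analysis forward.
- **The no-testing sentence need not conflict.** The protocol promises an assessment and names no test or p-value, so a descriptive estimate would satisfy both documents. This stands, and it shapes the fix.
- **Little power is gained.** This stands, as the working shows.
- **The trend can be computed at any time from data already collected.** True, but then the choice of outcomes and model is no longer prespecified.

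**Conclusion.** The point holds as a mismatch between protocol and SAP: a promised dose-response assessment of TEAEs has no counterpart in the SAP, in a dose-selection trial with tolerability among its primary objectives. It should be corrected. No efficacy result, error rate or data collection is affected.

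The mismatch rests on the text alone. The figures rest on assumed event rates and a linear trend in dose, whereas the protocol assumes only monotonicity. They show that the benefit is a prespecified slope with its uncertainty. They do not support the tempting claim that a trend analysis would detect what the SAP's intervals would miss. At modest gradients the active-dose slope will be imprecise (power about 16% to 20%), and the absence of a clear slope should not be read as equal tolerability.

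**What to change.** In SAP 6.1, add a descriptive dose-response estimate across the three active doses, for example the logistic regression slope on dose in mg with its 95% confidence interval and no p-value. Apply it to any TEAE, nausea, vomiting, diarrhea and adverse events leading to discontinuation. Label it descriptive, so that it sits with the no-testing sentence in SAP 6, and state that it implements protocol 9.4.2.

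If a version including placebo is also shown, add a note that it can be positive when rates are flat across active doses (about 71% of the time at assumed rates of 10/30/30/30%).

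If the sponsor prefers not to do the analysis, record this as a departure from the protocol with a reason.

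The cost is one extra table, whose slopes will have wide intervals if gradients are modest, or one entry in the SAP. No new data are needed.
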